
 LDH > 300 U/L, D-Dimers > 1000 ng/mL (fibrinogen equivalent units [FEU]) or > 2 times upper normal limit, C-reactive protein (CRP) > 70 mg/L 
 Change from baseline in cytokine profile (IL-1β, IL-10, IL-6, IL-8 IL-2, interferon γ, and tumor necrosis factor-α [TNF-α]) to Days 5, 15, and 29 
The safety variables include:
 
 Cumulative incidence of treatment-emergent serious adverse events (SAEs) and potentially related SAEs through Day 90 Phone Check Cumulative incidence of Grade 3-5 treatment-emergent adverse events (TEAEs) and potentially related severe TEAEs through Day 29 as defined in the Common Terminology Criteria for Adverse Events (CTCAE), US Department of Health and Human Services, National Institutes of Health (NIH), and National Cancer Institute (NCI) Cumulative incidence of all TEAEs and potentially related TEAEs through Day 29 
In this clinical study, disease progression is defined as the worsening of a subject's condition attributable to the disease for which the investigational product is being studied. It may be an increase in the severity of the targeted disease and/or increases in the symptoms of the targeted disease. Anticipated symptoms of COVID-19 include fever, cough, hypoxia, dyspnea, hemoptysis, myalgia, fatigue, pharyngitis, which may develop at any time during the course of the disease. The development of COVID-19 symptoms during the clinical study should not be recorded as individual TEAEs, unless there is evidence suggesting a causal relationship between Gamunex-C and the TEAE.
 
Study Assessments and Procedures:
 
A complete schedule of study procedures and events are located in Appendix 1.
 
Clinical status will be evaluated for all hospitalized subjects daily with vital signs, Ordinal Scale, and NEWS at Screening/Baseline and during IVIG plus SMT or SMT alone treatment and during Follow-up. The NEWS calculation is delineated in Appendix 2 and can be calculated using the on-line web tool at https://www.mdcalc.com/national-early-warning-score-news
 
All subjects will be followed daily through Day 10. After Day 10, if subjects are discharged from the hospital, evaluations at Day 15 and 29 are required. Berlin criteria for ARDS and SOFA score (Appendix 3 and Appendix 4) will be assessed on Day 1, 5, 15, and 29. Subjects remaining hospitalized will be followed daily through Day 29. Days 15\pm1 and 29\pm1 may be performed at the study site or, if deemed appropriate, at an alternate site (e.g., subject's residence, local healthcare professional's site) under the care and supervision of trained healthcare personnel. If an in-person visit is unable to be conducted for Day 15 or Day 29, the study site will make a phone call to the subject to obtain as much information as possible remotely (e.g., Ordinal Scale, clinical features key symptoms, supplementation oxygen use, SAEs and TEAEs, concomitant medications). Phone Checks will occur at Day
									

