7.2.2 Screening/Baseline and Randomized Treatment (Day 1)

All required screening and baseline (pre-infusion Day 1) procedures/assessments will be performed prior to administration of the IP (for subjects randomized to the combination arm).

Assessments include the following:

- Informed consent
- Inclusion/exclusion criteria
- Pregnancy test for females of child-bearing potential
- Record demography (age [year of birth], age at screening [years], gender [if female, fertility status], race, and ethnicity), disease characteristics (date of exposure, date of onset)
- Ordinal Scale assessment
- National Early Warning Score (NEWS) ([Appendix 2](#))

GRIFOLS Bioscience Industrial Group	Number	BLG-CL-PRT-000020	Version	4.0	Status	Effective	Effective Date	19-Jul-2021	49 of 91
	GC2007 - A Multicenter, Randomized, Open-label Parallel Group Pilot Study to Evaluate Safety and Efficacy of High Dose Intravenous Immune Globulin (IVIG) plus Standard Medical Treatment (SMT) versus SMT alone in								

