9 STATISTICS

9.1 Statistical Methods

Descriptive statistics will include the number of non-missing observations, mean, standard deviation (SD), median, minimum, and maximum values for the continuous/quantitative data or absolute and relative frequency counts and percentages for categorical/qualitative data. All statistical tests will be 2-sided at a significance level of 0.05.

An interim analysis will be conducted after 50 subjects (approximately 25 per group) for safety variables through Day 29. Due to the exploratory nature of this phase 2 study, the multiplicity adjustments will not be considered; full details will be described in the statistical analysis plan. This interim evaluation simply represents Sponsor safety due diligence.

There will be 3 analysis populations in this study; 2 populations for efficacy assessments and 1 population for safety evaluation.

The intention to treat (ITT) population is defined as all subjects who are randomized. The ITT population will be used for all efficacy analyses.

The Per-Protocol (PP) population is defined as the subset of subjects included in the ITT population who do not present major protocol violations which might have an impact on the primary efficacy endpoint, and complete at least 80% of the IP. The primary efficacy analyses will be carried out using the PP population if different from the ITT population.

The Safety population is defined as the subset of subjects who receive at least any amount of IVIG plus SMT or SMT alone. Safety analyses will be based on the Safety population.

The primary efficacy analysis will be carried out on the ITT population and repeated on the PP population (if different from the ITT population) by Fisher's exact test or Chi-square test. Secondary and exploratory efficacy analyses will be analyzed by means of Kaplan-Meier survival estimates and curves and compared between treatment groups by means of the Log-rank test for time to event variables, analysis of covariance (ANCOVA) or Student's t test for normally-distributed variables or Wilcoxon rank-sum test for non-normally-distributed variables. Detailed data handling and evaluation procedures and details of the interim reviews will be described in the Statistical Analysis Plan (SAP). The SAP may include exploratory analyses of various aspects of SMT inclusive of different interventional strategies and evolving treatment modalities.

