#### 4.6 Data Derivations and Transformations

The following derivations will be used in this study:

Study Day:

- Date of assessment – date of randomization + 1 for assessments done on or after date of randomization
- Date of assessment – date of randomization for assessments done before date of randomization

Baseline Observation: the last non-missing value prior to randomization.

Duration:

- Duration in days = end date – start date + 1
- Duration in minutes = end time in minutes – start time in minutes

Origin or Start Date for Time to Event Endpoints:

- Time to death: date of randomization
- Time to ICU Discharge (actual and medical equivalence, if applicable): date of randomization or date of ICU admission, whichever was later
- Time to Hospital Discharge (actual and medical equivalence, if applicable): date of randomization
- Time to Clinical Response: date of randomization

Event Date for Time to Clinical Response:

- If a subject met the criteria for clinical response at multiple assessments, the date of the first assessment meeting the definition of clinical response will be used as the event date for deriving time to clinical response.

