## 6.2 Secondary Efficacy Endpoints and Analyses

### Time to ICU discharge (Actual and Medical Equivalence)

Time to actual ICU discharge is defined as duration of actual ICU stay from Day 1 through Day 29 that is recorded on the eCRF All Visits page "General Duration of Hospitalization, & Overall Requirement for Mechanical Ventilation, ICU Admission and/or Oxygen Supplementation". The proportion of subjects who are discharged from the ICU will be estimated using the CIF. Deaths that occur prior to discharge from the ICU will be treated as a competing risk. The estimated cumulative incidence and associated two-sided 95% CI on Days 15 and 29 will be displayed. Test for equality of the CIF between treatment groups will be conducted using Gray's test.

Additionally, medical equivalence of ICU discharge date will be recorded on the eCRF if it is different from the actual ICU discharge date, and the time to medical equivalence of ICU discharge will be analyzed using the same method as described above. The proportion of subjects who are medical equivalence of discharge from the ICU will be estimated using the CIF. Deaths that occur prior to medical equivalence of ICU discharge will be treated as a competing risk. The estimated cumulative incidence and associated two-sided 95% CI on Days 15 and 29 will be displayed. Test for equality of the CIF between treatment groups will be conducted using Gray's test.

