### **Ordinal scales**

- a) The absolute value and change from baseline in the Ordinal scale from Day 1 through Day

29 will be summarized by treatment group and visit using descriptive statistics.

Mean change in Ordinal scales through Day 29 will be evaluated by fitting a linear mixed-effects model for repeated measures (MMRM). The model will include change from baseline in Ordinal scale as the repeated dependent variable; treatment (as a class variable), visit (as a class variable), and treatment-by-visit interaction as fixed effects; baseline Ordinal scale, age and gender as covariates; and measures within subject at each visit as a repeated measure. An unstructured covariance matrix will be used to model the within-subject error. If the fit of the unstructured covariance structure fails to converge, a compound symmetry covariance structure will be used. Parameters will be estimated using restricted maximum likelihood with the Kenward-Roger method for calculating the denominator degrees of freedom. Data collected starting at the Day 2 visit and up to the Day 29 visit will be included in this analysis. Missing data will not be imputed. From this model, the least-squares (LS) means and 95% CIs for each treatment group, the treatment difference in the LS means, the 95% CI for the difference, and the associated p-value will be reported on Days 15 and 29, as well as for the average across all post-baseline visits.

- b) The proportion of subjects in each severity category of the 7-point Ordinal scale at Day 15 and Day 29 will be tabulated. The difference in severity category distribution between treatment groups at Day 15 and Day 29 will be examined using proportional-odds cumulative logit model. The cumulative logits model will compare lower ordinal scales to higher ones, or equivalently, less favorable outcomes to more favorable ones. The model may be adjusted for baseline characteristics such as age and gender, if appropriate. The estimated odds ratio and 95% CI will be presented. Graphical illustrations of the fitted model will also be presented for Day 15 and Day 29.

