### **Assessment of clinical severity**

The NEWS will be calculated based on 7 clinical parameters and recorded on the eCRF. The absolute value and change from baseline in the total score from Day 1 through Day 29 will be summarized by treatment group and visit using descriptive statistics.

Change in NEWS total score through Day 29 will be evaluated by fitting a linear MMRM. The model will include change from baseline in NEWS total score as the repeated dependent variable; treatment (as a class variable), visit (as a class variable), and treatment-by-visit interaction as fixed effects; baseline NEWS total score, age and gender as covariates; and measures within subject at each visit as a repeated measure. An unstructured covariance matrix will be used to model the within-subject error. If the fit of the unstructured covariance structure fails to converge, a compound symmetry covariance structure will be used. Parameters will be estimated using restricted maximum likelihood with the Kenward-Roger method for calculating the denominator degrees of freedom. Data collected starting at the Day 2 visit and up to the Day 29 visit will be included in this analysis. Missing data will not be imputed. From this model, the least-squares (LS) means and 95% CIs for each treatment group, the treatment difference in the LS means, the 95% CI for the difference, and the associated p-value will be reported on Days 15 and 29, as well as for the average across all post-baseline visits.

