### **Time to clinical response**

Clinical response is defined as the NEWS score <=2 maintained for 24 hours from Day 1 through Day 29. The time to the first occurrence of clinical response will be estimated using the Kaplan-Meier (KM) method. The KM estimates along with 95% CI, and survival curves will be provided. Based on the KM estimates, the probabilities of achieving first clinical response and associated 95% CIs on Days 15 and 29 will be reported; in addition, the 25th, 50th (median), and 75th percentiles of the time to first clinical response with associated 95% CIs will be provided, as data permit. The survival rates between treatment groups will be compared using Log-rank test. The p-value from Log-rank test will be presented.

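### Time to clinical response and time to discharge are compared without baseline adjustment, giving up power that the recorded baseline NEWS and Ordinal scale could recover

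*SAP*

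**What the plan says.** SAP 6.2, Time to clinical response, defines response as a NEWS of 2 or less held for 24 hours, reports Kaplan-Meier estimates by arm and adds: "The survival rates between treatment groups will be compared using Log-rank test". SAP 6.2, Time to ICU discharge, says "Test for equality of the CIF between treatment groups will be conducted using" Gray's test, with death competing; the hospital discharge section does the same. Each covers an actual and a medical-equivalence version, so there are four discharge endpoints. No covariate, stratum, Cox model or Fine-Gray model is named for any of the five. Protocol 9.1 likewise has treatment groups "compared between treatment groups by means of the Log-rank test for time to event variables".

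The baseline scores exist. The protocol synopsis says "Clinical status will be evaluated for all hospitalized subjects daily with vital signs, Ordinal Scale, and NEWS at Screening/Baseline", and SAP 4.6 fixes the value to use: "Baseline Observation: the last non-missing value prior to randomization". The repeated-measures models in the same SAP section require them: the NEWS model has "baseline NEWS total score, age and gender as covariates" and the Ordinal model has "baseline Ordinal scale, age and gender as covariates".

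Protocol 4.3.2 describes one central list, used from the top, with no stratification factor. SAP 9 gives about 100 subjects and no power, effect size or event rate.

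**The concern.** By their definitions, these endpoints depend on where a subject starts. Response is a threshold on the same score that is measured at baseline, and supplemental oxygen alone contributes 2 NEWS points (Protocol Appendix 2). Eligibility admits subjects on mechanical ventilation or on supplemental oxygen, so they can start in Ordinal categories 2 to 4. Medical equivalence of ICU discharge requires, among other things, being off invasive ventilation and needing no more oxygen than a nasal cannula delivers. Medical equivalence of hospital discharge requires no supplemental oxygen. Baseline score therefore measures distance from the event.

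Leaving a prognostic factor out of a log-rank or Gray's comparison costs power. With about 50 per arm and no stated stratification, a chance difference in severity can also influence a single result noticeably. In addition, the plan yields only per-arm curves, probabilities or percentiles and a p-value for these endpoints. A pilot would normally want a between-arm estimate with an interval to plan what follows.

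**Working it through.** The plan states no power or event count for any endpoint, so there is no figure to reproduce.

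**1. Where adjustment is and is not provided (SAP 6.2)**

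- Change in NEWS, Ordinal scale and SOFA: baseline score, age and gender required.
- Ordinal distribution at Days 15 and 29: adjustment optional.
- Durations of ICU stay, hospitalization, ventilation and oxygen use: optional ANCOVA, with age and gender as examples and no severity score named.
- Time to clinical response and the four discharge times: none.

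Among the formally tested secondary endpoints, only the last group has no adjustment provision. SAP 5.6 allows post-hoc adjustment, but only for imbalance in COVID-19 medication use.

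**2. Chance imbalance**

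With 50 per arm, the standard error of the baseline difference is √(1/50 + 1/50) = 0.20 SD. The probability that the absolute difference exceeds x is 2[1 − Φ(x/0.20)]:

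- x = 0.2 SD: 32%
- x = 0.3 SD: 13%
- x = 0.4 SD: 5%

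In null simulations (2,500 trials per setting, no competing deaths), the unadjusted log-rank test rejected in 4.5% to 5.8% of trials overall. Among trials with imbalance above 0.3 SD, it rejected in about 7% to 9% when the score's log hazard was 0.5 per SD, and about 10% to 15% at 0.8 to 1.0.

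**3. Power**

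All inputs here are assumed: 100 subjects 1:1, control median 14 days to event, about 30% deaths at average risk, cause-specific hazard ratio 1.8, two-sided 5% level. The standardised baseline score acts with log hazard β per SD, in opposite directions on the event and on death. The correlation with log time is β/√(β² + 1.645); for example 0.41/√(0.168 + 1.645) = 0.30 and 0.74/√(0.548 + 1.645) = 0.50.

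Clinical response is run with deaths censored, as SAP Table 1 specifies. Discharge is run with deaths kept at risk to Day 29, which matches the subdistribution approach.

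| β per SD | Response: unadjusted → adjusted | Discharge: unadjusted → adjusted |
|---|---|---|
| 0.30 | 66% → 69% (+3) | 56% → 60% (+4) |
| 0.41 | 62% → 69% (+7) | 54% → 60% (+6) |
| 0.50 | 61% → 72% (+11) | 47% → 59% (+12) |
| 0.74 | 48% → 67% (+19) | 40% → 57% (+17) |

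At β = 0 with deaths kept at risk the figures are 61% unadjusted and 60% adjusted, so nothing is lost. Type I error is 4% to 6% for both approaches. Simulation error is a point or two per cell.

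**4. Checks**

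Schoenfeld's approximation, Φ(√E × ln HR / 2 − 1.96), with E = 70 events and HR 1.8 gives Φ(8.37 × 0.588 / 2 − 1.96) = Φ(0.50) = 69%. With E = 75 it gives 72%. The adjusted response figures (67% to 72%) lie close to this.

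A separate log-rank versus Cox simulation without competing deaths shows the same pattern at hazard ratio 1.75:

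- β = 0.5: 53% → 61% with 60% control response, 42% → 47% with 40%.
- β = 0.8: 44% → 61% and 36% → 47%.

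**The case against.** The strongest reply is that nothing here is wrong. Log-rank and Gray's tests are valid under simple randomization, their p-values already allow for chance imbalance, and the protocol names log-rank for time-to-event variables. These are secondary endpoints in an exploratory pilot with no power target and no multiplicity control. All of that stands, and it makes this a point about efficiency.

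Four stronger readings may tempt a reader, and the documents do not support them.

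- **That the unadjusted tests are biased or inflate alpha.** Averaged over randomizations they do not. The raised error in step 2 is conditional on an imbalance having occurred.
- **That the planned effect estimates are shrunk towards 1.** The SAP plans no hazard ratio for these endpoints, and a marginal and a covariate-conditional ratio are different quantities in any case.
- **That the discharge tests contradict their companion models.** The nearest companions, the ICU-stay and hospitalization durations, allow only optional adjustment. Required baseline-score adjustment is confined to the repeated-measures models.
- **That the power figures with deaths kept at risk apply to clinical response.** Table 1 censors those deaths, and under that rule the unadjusted test has about 8 to 14 points more power than the discharge column shows.

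It is also fair that eligibility narrows the baseline spread and that no document gives the prognostic strength. A gain near the lower end of the table is therefore quite possible.

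**Conclusion.** The point holds as a weakness in efficiency and reporting. Five secondary comparisons omit baseline scores that the trial collects and that the same SAP requires elsewhere. Under the stated assumptions the cost is about 3 to 19 points of power for clinical response and 4 to 17 points for discharge, rising with how prognostic the score is and vanishing if it is not prognostic. Sensitivity to chance imbalance and the lack of a between-arm estimate add to the case. The direction follows from how the endpoints are defined; the size depends entirely on assumed event rates, effect and prognostic strength. One might expect adjustment to bring the time-to-event and repeated-measures results into agreement. It need not, because they answer different questions.

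**What to change.** Name one model per endpoint in SAP 6.2 before outcome data by arm are examined.

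- **Time to clinical response:** a Cox model with treatment, baseline NEWS, age and gender, under the existing Table 1 censoring rule.
- **Time to ICU and hospital discharge, actual and medical equivalence:** a Fine-Gray model with death competing and with treatment, baseline Ordinal category, age and gender.

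Report the adjusted ratio with its 95% CI and p-value as the between-arm comparison. Keep the Kaplan-Meier and cumulative incidence curves and the log-rank and Gray's tests as supportive. Record the change from the method named in Protocol 9.1.

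The cost is SAP wording and a few model runs on data already collected. The downsides are a proportional hazards assumption (proportional subdistribution hazards for discharge) and an estimate that is conditional on the covariates; the supportive unadjusted tests give a check free of both. Prespecification matters because the trial is open-label, and adjustment added after an imbalance is seen would be open to challenge.

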## **6.3 Exploratory Efficacy Endpoints and Analyses**

- Change from baseline in quantitative SARS-CoV-2 viral load by NAT or PCR (RT-PCR) to Days 5, 15, and 29 will be summarized for each treatment group by visit.
- Change from baseline in quantitative anti- SARS-CoV-2 IgM and IgG antibodies to Days 5, 15, and 29 will be summarized for each treatment group by visit.
- The proportion of subjects with evidence of hyperinflammation on Days 1, 5, 15, and 29 will be tabulated by treatment group. For this analysis, the denominator for calculating the

proportion at each visit and within each treatment group will be the number of subjects with non-missing values for Lymphocyte counts AND for at least 2 of the following 4 lab parameters: Ferritin, LDH, D-Dimers, and C-reactive protein (i.e., the number of subjects for whom evidence of hyperinflammation could be assessed).

- Change from baseline in cytokine profile (IL-1 $\beta$ , IL-10, IL-6, IL-8 IL-2, interferon  $\gamma$ , and TNF- $\alpha$ ) to Days 5, 15, and 29 will be summarized for each treatment group by visit.

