#### 2.1.3 Exploratory Efficacy Objectives

The exploratory objectives of the study are:

- To evaluate the effect of high dose IVIG plus SMT versus SMT alone with regard to quantitative severe acute respiratory syndrome coronavirus 2 (SARS-CoV-2) viral load and anti-SARS-CoV-2 antibodies in hospitalized subjects with COVID-19.
- To evaluate whether high dose IVIG plus SMT versus SMT alone reduces the frequency of hyperinflammation based on a pre-specified biochemical definition through Day 29.
- To evaluate cytokine profile changes from baseline for high dose IVIG plus SMT versus SMT alone through Day 29.

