## 4. GENERAL CONSIDERATIONS FOR DATA ANALYSIS

Unless otherwise specified, continuous variables will be summarized using descriptive statistics (n, mean, standard deviation, median, minimum, and maximum). Categorical variables will be summarized showing the number and percentage of subjects within each category.

Summary results will be provided for each treatment group. All tabulations will be based on pooled data across centers.

All statistical tests will be two-sided and tested at the 5% level of significance.

Analyses will be performed using SAS for Windows statistical software, version 9.4 or higher (SAS, Cary, NC), except where other software may be deemed more appropriate. In the event that other software is used to perform some analyses, the details will be provided in the Clinical Study Report.

■ will perform all efficacy and safety analyses described in this SAP.

Subject data will be listed, sorted by treatment group and subject number. When applicable, listings will be additionally sorted by visit and assessment date/time.

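### SAP 6.3 drops the between-arm comparison that Protocol 9.1 states for exploratory efficacy analyses and names no analysis scale, so the IVIG-versus-SMT exploratory objectives get no estimate or confidence interval

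*SAP*

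**What the plan says.** The exploratory objectives in SAP 2.1.3 (the same in Protocol 3.1.3) are comparative. One begins "To evaluate the effect of high dose IVIG plus SMT versus SMT alone with regard to quantitative" and goes on to viral load and antibodies. Another reads "To evaluate cytokine profile changes from baseline for high dose IVIG plus SMT versus SMT alone through Day 29". The third asks whether IVIG lowers the frequency of hyperinflammation relative to SMT alone.

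Protocol 9.1 covers secondary and exploratory efficacy analyses in one sentence: Kaplan-Meier and log-rank for time-to-event variables, ANCOVA or Student's t test for normally distributed variables, or "Wilcoxon rank-sum test for non-normally-distributed variables".

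SAP 6.3 plans less. For viral load, change in "viral load by NAT or PCR (RT-PCR) to Days 5, 15, and 29 will be summarized for each treatment group by visit". For antibodies, change in "IgM and IgG antibodies to Days 5, 15, and 29 will be summarized for each treatment group by visit". The seven cytokines have the same wording. For hyperinflammation: "The proportion of subjects with evidence of hyperinflammation on Days 1, 5, 15, and 29 will be tabulated by treatment group", among subjects with enough laboratory values to be classified.

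Unless otherwise specified, SAP 4 says that "continuous variables will be summarized using descriptive statistics (n, mean, standard deviation, median, minimum, and maximum"). SAP 4.6, whose title covers derivations and transformations, opens "The following derivations will be used in this study" and then lists only study day, baseline, duration, time origins and one event date.

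**The concern.** A per-arm summary is not an estimate of a treatment effect. With two columns of descriptive statistics, the reader must subtract by eye and gets no measure of uncertainty. The protocol's rationale (2.3.2 and 2.7.1) is that high-dose IVIG modulates the inflammatory cascade, and these endpoints bear directly on that.

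The missing scale adds a second problem. Viral load can plausibly spread over orders of magnitude, as may antibody and cytokine levels. If it is summarised as untransformed copies, the change from baseline is an absolute fall in copies, not a fold reduction, and it is weighted toward subjects with very high values. Comparing two such means, or even two such medians, can then suggest the wrong arm.

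**Working it through.** **1. The texts side by side.**

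| Item | Comparative objective? | Protocol 9.1 | SAP |
|---|---|---|---|
| Viral load, IgM/IgG, seven cytokines | Yes | ANCOVA, t test or Wilcoxon | 6.3: per-arm summary only |
| Hyperinflammation | Yes | No method named for a secondary or exploratory proportion | 6.3: per-arm tabulation only |
| SOFA change (secondary), same Days 5, 15, 29 | Yes | Same sentence as above | 6.2: MMRM, LS-mean difference, 95% CI, p-value |
| Safety | Yes | No test named | 7: formal between-group testing expressly excluded |

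None of the exploratory endpoints is a time to event. For them, the operative part of the Protocol 9.1 sentence is therefore ANCOVA, t test or Wilcoxon, all of which are between-arm methods. SAP 6.3 neither carries them over nor says that they are dropped. Where the SAP wants no comparison (safety), it says so.

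**2. Does the missing scale matter?** The documents give no variance, effect size or power for these endpoints, so there is no planned figure to reproduce. The simulation below covers viral load only, and all its inputs are assumptions: 45 sampled subjects per arm (about 50 are randomised per arm); baseline log10 load B ~ N(6, SD²); log10 change G ~ N(−1, 1) on SMT and N(−1.5, 1) on IVIG, a true extra fall of 0.5 log10. Untransformed change is 10^(B+G) − 10^B. A summary is wrong when it shows the larger fall on SMT. There were at least 20,000 trials per setting.

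| Baseline log10 SD | Mean change wrong | Median change wrong | Mean log10 change wrong |
|---|---|---|---|
| 0.3 | 14% | 19% | 1% |
| 0.5 | 19% | 22% | 1% |
| 1.0 | 32% | 26% | 1% |
| 1.5 | 39% | 27% | 1% |
| 2.0 | 41% | 29% | 1% |

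The last column has a closed form: Φ(−0.5/√(2/45)) = Φ(−2.37) = 0.009.

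With a true extra fall of 1.0 log10 and SD 1 to 2, the mean is wrong in about 25 to 37% and the median in about 17 to 20%. At SD 0.3 to 0.5 the mean is wrong in about 3 to 7%. The log10 mean is practically never wrong.

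**3. A different model.** Take 50 per arm, baseline/follow-up correlation 0.5, a mean fall of 1 log10 on SMT, and true effects of 0.2, 0.3, 0.6 and 0.9 log10 at SD 0.3, 0.5, 1.0 and 1.5. The arm difference has the right sign in 55 to 60% of trials for means of untransformed change, 61 to 74% for medians, and about 100% for log10 means.

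**4. How concentrated is the mean?** In the step 3 model, the two largest contributors supply a median 14%, 24%, 53% and 73% of an arm's total absolute change at SD 0.3, 0.5, 1.0 and 1.5. Two subjects carry about half or more only when the log10 SD is about 1 or higher.

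**5. What a between-arm estimate would deliver.** For log10 ANCOVA with baseline correlation 0.5, the 95% CI half-width is t(0.975, 2n−3) × SD × √0.75 × √(2/n). For n = 50 and SD 1.0 this is 1.985 × 0.866 × 0.2 = 0.34 log10, so the CI is the ratio times or divided by 10^0.344 = 2.21. At SD 0.5 and 1.5 the factors are 1.49 and 3.28. If only 35 or 25 per arm are sampled at SD 1.0, they are 2.59 and 3.11.

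**The case against.** The strongest defence is that these are exploratory endpoints in a pilot. SAP 4.5 makes no multiplicity adjustment, and describing biomarkers without testing is a respectable choice. That stands as a reason to grade the point low. It does not explain the gap, because Protocol 9.1 names comparative methods for exploratory analyses and SAP 6.3 does not say why it departs from them.

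A reader might infer that the SAP fixes these analyses on the raw scale. It does not. SAP 4 and 6.3 name no scale, and SAP 4.6 is silent. The assays are run centrally (Protocol Table 7-1) with the antibody method left open, so values might arrive as log10 or Ct. The supportable statement is that no scale is specified.

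A reader might also infer that the means will be driven by one or two subjects. That depends on a spread the documents do not give, and at log10 SD 0.3 to 0.5 it is not so. Nor is the mean the only planned summary: the median is listed, and at SD 1 or more it errs less often than the mean, though still far more often than the log10 mean.

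Finally, these assays are not the trial's only evidence on mechanism. Hyperinflammation, built from lymphocytes, ferritin, LDH, D-dimer and CRP, is a separate exploratory endpoint, and SAP 7.3 summarises laboratory changes by arm.

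**Conclusion.** The point holds as a mismatch between the documents and needs no assumption: Protocol 9.1 states a between-arm comparison, SAP 6.3 omits it, and the comparative exploratory objectives are left without an estimate or interval. Even if the laboratory reports log10 values, that gap remains.

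The second part is conditional. If viral load is analysed as untransformed copies, mean change can be a poor guide to the arm effect, and the median helps only partly. The error rates rest on log-normal data, the assumed SDs and effects, and 45 sampled per arm. They were not computed for antibodies or cytokines and should not be read across to them.

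Severity is minor. This is a cheap improvement, and the primary mortality analysis is untouched.

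**What to change.** Reconcile SAP 6.3 with Protocol 9.1, and state the analysis scale for each assay.

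- **Viral load, IgM/IgG, cytokines:** at Days 5, 15 and 29, analyse log10 values by ANCOVA adjusted for log10 baseline (or by MMRM as already planned for SOFA). Report the IVIG/SMT geometric mean ratio with 95% CI. If the laboratory already delivers log10 or Ct values, use that scale without a second transformation.
- **Values below the assay limit:** state the handling rule, use Wilcoxon where many values fall below the limit, and show the number below the limit and the number sampled per arm and visit.
- **Deaths:** say that the results describe survivors with samples, and show deaths before each visit by arm. A baseline-adjusted ratio does not remove this selection.
- **Hyperinflammation:** add the risk difference with 95% CI at each post-baseline visit, on the denominator SAP 6.3 already defines.
- **Status:** label all of these exploratory and unadjusted for multiplicity. Intervals without p-values would suit that status.

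The log-scale ratio and the risk difference go beyond what Protocol 9.1 names, so they are additions and should be presented as such. The cost is SAP wording and a few extra tables, with no new samples or visits.
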